6.5 TREATMENT DURATION

Patients will receive trial treatment until one of the following criteria applies:

- disease progression,
- unacceptable toxicity or toxicity that results in treatment interruption of >4 weeks,
- patient experiences DLT

- patient decides to withdraw from study, starts a new therapy or is lost to follow up
- discontinuation from the study treatment for any other reason.
- PI or study sponsor discretion

Patients who come off therapy will be followed for survival regardless of cause of treatment discontinuation.”

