6.6 DOSE LIMITING TOXICITIES-PHASE IB COMPONENT

The phase Ib component of the study will consist of 3+3 dose escalation rule with the dose of LEE011 escalating up to 600mg daily to determine the maximum tolerated dose (MTD) that will be used during the phase II component. The dose levels for the phase Ib aspect will be 200 mg, 400 mg, or 600 mg daily.

Only the first cycle of therapy (one cycle equals to one month) will be used to determine dose limiting toxicity (DLT). However, if two total grade 5 adverse events or 2 Grade 4 adverse events (lasting ≥ 7 days); occur at any time while the patient is still receiving study treatment that are either: definitely, probably, or possibly related to either LEE011 or TACE the study will be terminated to enrollment.

Only patients started on the first dose of LEE011 will be included in the evaluation of DLT. If a patient has a DLT that patient will not receive further LEE011. Patients following initial chemoembolization who never receive LEE011 will not be included in the MTD analysis and will be replaced. The patients will be followed for thirty days following the initial chemoembolization for safety assessment. Patients will be enrolled into the next highest drug cohort only after 3 or 6 patients have completed the first cycle of therapy. Once the MTD is determined, patients at the MTD dose will continue with LEE011 and represent the first three patients accrued to the phase II aspect.

Due to observed (TACE related, non DLT) toxicity on cohort 1 specific criteria for cohort 1 has been developed after discussion with the FDA. Cohort 1 has been expanded to 6 patients. Decision for dose escalation will be made using the following criteria:

- No or one DLT: the next three patients will be assigned to next higher dose level (400 mg of LEE011).
- At least two toxicities: the MTD is exceeded and the phase I component of the trial will be stopped with no continuation into the phase II component.

For Cohort 2 and 3 the following traditional 3+3 dose escalation rules will be used:

- If a dose limiting toxicity (DLT) is observed in 1 out of 3 patients at a given dose level, up to 3 additional patients will be enrolled and treated at that dose level.
- If 2 out of 3-6 patients at that dose level have DLTs, the dose will be decreased to the previous dose level, and up to 3 additional patients will be enrolled at that dose level for a total of 6 patients.

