- When up to 3 additional patients are added to a given dose level, if 0-1 of 6 patients has a DLT then the dose will be increased to the next dose level.
- Additional dose levels may be explored per investigator discretion to define the safety profile of the treatment.

The recommended Phase II dose (RP2D) will be the highest cohort level in which one or fewer subjects of 6 develops a first cycle DLT.

The Data and Safety Monitoring Committee as described below will regularly review all serious adverse events and any local adverse events, which are unanticipated problems. The study will utilize the Common Terminology Criteria for Adverse Events (CTCAE) version 4.03 for grading of all adverse events related to treatment.

Table 6.2: Dose-limiting toxicity: phase Ib component

The following will be considered a DLT if they occur within the first cycle of therapy with LEE011 and are determined to be possibly, probably or definitely related to LEE011

Grade 4 neutropenia lasting more than 7 consecutive days
Grade 3 or 4 febrile neutropenia
≥ Grade 3 vomiting ≥ 48 hours despite optimal anti-emetic therapy
≥ Grade 3 diarrhea ≥ 48 hours despite optimal anti-diarrhea therapy
Clinical signs of cardiac disease, such as unstable angina or myocardial infarction, or Troponin ≥ grade 3
Grade 4 serum alkaline phosphatase > 7 days
≥ Grade 3 serum creatinine
≥ Grade 3 adverse event for any non-hematologic toxicity unless otherwise specified as below (excluding alopecia, fatigue < 5 days, laboratory abnormalities that are responsive to oral supplementation or deemed by the investigator to be clinically insignificant).

THROMBOCYTOPENIA	
Toxicity/Grade	Dose Limiting Toxicity and Management Recommendations
Grade 3 ($\geq 25 \times 10^9/L$ - $<50 \times 10^9/L$) without clinically significant bleeding	Dose interruption until recovery to grade ≤ 2 . Re-initiate LEE011 at the same dose level. • If toxicity recurs at grade 3: dose limiting toxicity
Grade 3 ($\geq 25 \times 10^9/L$ - $<50 \times 10^9/L$) with clinically significant bleeding	Dose limiting toxicity
Grade 4 ($<25 \times 10^9/L$)	Dose limiting toxicity

HEPATOTOXICITY (BILIRUBIN, ALT, AST)	
TOTAL BILIRUBIN without ALT/AST increase above baseline value	
Toxicity/Grade	Dose Limiting Toxicity and Management Recommendations
Same grade as baseline or increase from baseline grade 0 to grade 1	Maintain dose level with LFTs monitored every other-week

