12.0 STATISTICAL CONSIDERATIONS

12.1 STUDY DESIGN/STUDY ENDPOINTS

The study is an open-label, non-randomized single-arm, single institution phase Ib/II therapeutic clinical trial. The study population will be patients with advanced hepatocellular carcinoma.

The phase Ib component of the study will consist of a traditional 3+3 dose escalation rule with 3 or 6 patients in each cohort, the process for dose escalation is outline in section 6.4.

The primary endpoint of the phase II component will be progression free survival (PFS) of

HCC patients. PFS is defined to be the time from initiation of treatment to progression or death without evidence of progression. For cases without documentation of progression, follow-up will be censored at the date of last disease assessment without progression, unless death occurs within 4 months following the date of last progression-free, in which case death will be counted as an event. The historical median PFS for TACE alone is 8-10 months. Our institutional median PFS following the TACE protocol outlined is 8.0 months. This study will target a hazard ratio of 0.69 with an 80% power and a one-sided significance level of 10%. Assuming a 24-month accrual and an 18-month follow-up period the study requires 38 patients initiating LEE011 treatment with the median PFS for TACE alone is 8 months, and 40 patients with the median PFS for TACE alone is 10 months. PFS will be estimated using the Kaplan-Meier method, and Greenwood's formula will be used to calculate the standard error of the corresponding Kaplan-Meier estimate and 95% confidence interval. Survival curves will be estimated using Kaplan-Meier methodology. Forty total patients will be enrolled in the phase II aspect of the trial. This includes only patients who undergo chemoembolization and initiate LEE011 therapy.

Secondary endpoints of efficacy are to evaluate OS. The statistical methods used for the analysis of PFS will be used for the analysis of OS.

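### Sections 6.6 and 12.1 disagree on which phase Ib patients enter the phase II PFS set; read literally, Section 6.6 favours patients still on treatment

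*Combined protocol and SAP*

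**What the plan says.** Section 6.6 (phase Ib dose-limiting toxicities) carries some phase Ib patients into phase II: after the MTD is determined, "patients at the MTD dose will continue with LEE011 and represent the first three patients accrued to the phase II aspect". Three other rules bear on who those patients can be.

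- Section 6.6 also states: "If a patient has a DLT that patient will not receive further LEE011". Section 6.5 lists disease progression, DLT, prolonged interruption for toxicity and withdrawal among the events that end trial treatment.
- Section 6.6 sets the recommended phase II dose as "the highest cohort level in which one or fewer subjects of 6 develops a first cycle DLT". That implies six patients at the dose, five or six of them without a DLT.
- After two DLTs in cohort 2 or 3, "the dose will be decreased to the previous dose level, and up to 3 additional patients will be enrolled at that dose level". The MTD can therefore be a dose whose first patients were treated before a higher cohort opened.

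Section 12.1 describes the phase II set differently. "Forty total patients will be enrolled in the phase II aspect of the trial", and "This includes only patients who undergo chemoembolization and initiate LEE011 therapy". Membership there depends on starting LEE011, not on continuing it.

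Sections 3.1 and 12.1 measure PFS from initiation of treatment. Section 2.1.2 uses the enrollment date. Both come before the MTD is known.

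**The concern.** A patient at the MTD who has already had a DLT, progressed, died or stopped cannot continue LEE011, so does not fit the sentence in Section 6.6. The same patient does fit Section 12.1. If Section 6.6 is followed, the carried-over patients are known to be on treatment, and so event-free, when they are counted, yet their PFS clock started earlier. The time in between is event-free by construction.

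There is also a choice of three from about six, with no rule for making it, in an open-label trial where outcomes are visible. At stake is the primary endpoint: a single-arm PFS estimate compared with a fixed historical median of 8 months, with no concurrent control carrying the same selection. Any such error favours the combination.

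**Working it through.** **1. The plan's own sample size.** Inputs from Section 12.1: hazard ratio 0.69, power 80%, one-sided 10%, 24 months' accrual, 18 months' follow-up, null median 8 or 10 months.

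- Events: (1.2816 + 0.8416)² / ln(0.69)² = 32.7.
- Event probabilities with exponential PFS and uniform accrual: 0.912 (null) and 0.819 (alternative) for an 8-month null median; 0.860 and 0.749 for 10 months.
- N = [(1.2816/√p0 + 0.8416/√p1) / ln(0.69)]² = 37.5 and 40.3, against 38 and 40 in the plan.

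The design is reproduced, and the carry-over question does not make it wrong.

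**2. How long the guaranteed time could be.** The documents do not give it, so a range is needed.

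- *Highest tested dose is the MTD.* LEE011 starts at the earliest 7 days after chemoembolization and cycle 1 lasts 28 days. The last patient therefore waits at least 35 days, about 1.15 months.
- *A lower dose becomes the MTD after a higher cohort is tested.* No phase Ib accrual rate is stated. Assume the phase II planning rate, 40/24 = 1.67 a month. Enrolling three to six patients at the higher dose takes 3/1.67 = 1.8 to 6/1.67 = 3.6 months. Adding 1.15 months to finish the last cycle 1 gives 2.95 to 4.75 months. Adding the lower-dose patient's own 1.15 months gives about 4.1 to 5.9 months.
- *A top-up of three more patients at the lower dose* would add about 3 months to the wait of the earlier patients, but the added patients themselves wait only about one cycle. The result then depends on which three are counted, which the plan does not say.

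**3. Effect on the comparison.** The plan names no test against the historical median, so a modified one-sample log-rank test is assumed: Z = (E − D)/√((E + D)/2), where D is observed events and E = (ln 2 / 8) × total follow-up, rejecting if Z > 1.2816. PFS is exponential with a true median of 8 months (no benefit), N = 40, and three patients are event-free for their first d months. There were 200,000 simulated trials per row. The apparent median solves (37/40)·2^(−t/8) + (3/40)·2^(−(t−d)/8) = 0.5.

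| d (months) | False-positive rate, log-rank | Same, log-hazard Wald test | Apparent median (months) |
|---|---|---|---|
| 0 | 9.7% | 8.6% | 8.0 |
| 1 | 10.6% | 9.4% | 8.1 |
| 2 | 11.1% | 9.8% | 8.2 |
| 4 | 12.6% | 11.3% | 8.35 |
| 6 | 14.3% | 12.8% | 8.6 |

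Repeat runs moved the log-rank column by no more than about 0.2 points.

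**4. How often the conflict would arise.** With an 8-month median, the chance that at least one of three patients has an event within d months is 1 − 2^(−3d/8): 23% at 1 month, 41% at 2 and 65% at 4. Detection will lag, because Section 8.0 schedules scans every 8 weeks.

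**The case against.** The strongest reply is that no exclusion rule exists. A reader might infer that MTD patients enter phase II only if they are still on LEE011, so that immortal-time bias is built into the design. The documents do not say that. Section 6.6 does not state that patients who stopped are dropped, Section 12.1 would keep them, and the first three could simply mean the first three by date. If only three patients were treated at the MTD and all continued, nothing would be selected. This reply stands as far as it goes: the exclusion is a literal reading of one sentence, not a declared rule. It does not remove the conflict with Section 12.1 or supply a way to take three from six.

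A reader might also infer that patients with a DLT vanish from the safety results at the recommended dose. They do not: Sections 3.1, 8.2 and 12.1 base safety on every treated patient. Nor is their PFS lost, because Section 7.4.3 continues scans after treatment stops for reasons other than progression.

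The size also depends on the path. If the MTD is declared soon after the last cycle 1, the latest patients have had no scheduled scan and are selected on little more than DLT, death or another early stop. At the recommended dose at most one patient in six has a first-cycle DLT, and leaving that patient out biases PFS only if DLT and PFS are associated.

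**Conclusion.** The point holds as a conflict between Sections 6.6 and 12.1 that affects the primary analysis set, with a direction of error that favours the combination if Section 6.6 is followed literally. It is not evidence that the plan deliberately selects on outcome, and it leaves safety reporting and the sample size untouched.

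The bias is modest: about one to one and a half points on the one-sided error for one to two months of guaranteed time. About three to five points arises only if a lower dose becomes the MTD after a higher cohort is tested and the earlier patients are the ones carried over. If Section 12.1 is applied to everyone who started at that dose, it is zero. These sizes rest on exponential PFS with an 8-month median, the assumed test, an assumed phase Ib accrual rate, and three of 40 patients affected. The matter should be settled before phase Ib outcomes are used to fill the phase II set.

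**What to change.** Reconcile Sections 6.6 and 12.1 by replacing the carry-over sentence in Section 6.6 with a rule along these lines: all phase Ib patients who started LEE011 at the dose chosen for phase II count toward the 40 and enter the PFS and OS analyses from their own start of treatment, whatever DLT, progression or discontinuation follows. Add a sensitivity analysis restricted to patients enrolled after phase II opened. Section 4.0 already gives both phases the same population, so no eligibility change is needed, and no dose or treatment rule is touched.

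The total stays at 40, and the false-positive rate returns to its no-selection value (9.7% in the table above). If six patients count instead of three, three fewer new patients are needed. The costs are one sentence, one extra analysis on a smaller set (40 − 6 = 34 if six count), and a PFS estimate that may be slightly less favourable. Excluding phase Ib patients altogether would also remove the problem, but needs 40 new patients; analysing only 37 would lower power from 0.80 to about 0.78 (Φ(√(37 × 0.819) × 0.371 − 1.2816)).

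### Section 6.6: the cohort 1 stopping branch counts toxicities while its paired escalation branch counts DLTs, so the same data can meet both

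*Combined protocol and SAP*

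**What the plan says.** Section 6.6 introduces a special rule for the first dose level with the words "Due to observed (TACE related, non DLT) toxicity on cohort 1". It reports that the criteria followed a discussion with the FDA and that the cohort was enlarged to 6 patients. Two branches follow:

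- Escalate: "No or one DLT: the next three patients will be assigned to next higher dose level", which is 400 mg.
- Stop: "At least two toxicities: the MTD is exceeded and the phase I component of the trial will be stopped", and the trial does not go on to phase II.

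The other decision rules in the section use DLTs. For cohorts 2 and 3, de-escalation is triggered by "If 2 out of 3-6 patients at that dose level have DLTs". The recommended phase II dose is the highest level at which "one or fewer subjects of 6 develops a first cycle DLT".

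DLT is a restricted term. On timing, "Only the first cycle of therapy (one cycle equals to one month) will be used to determine dose limiting toxicity (DLT"). Table 6.2 opens with "The following will be considered a DLT if they occur within the first cycle of therapy with LEE011", requires at least a possible relation to LEE011, and lists the qualifying events and grades.

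A separate safety stop in 6.6 closes enrolment "if two total grade 5 adverse events or 2 Grade 4 adverse events" occur. The grade 4 events must last at least 7 days, and the events must be at least possibly related to LEE011 or TACE. Section 9.4 has a parallel rule.

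**The concern.** The two cohort 1 bullets should divide the possible results between them, but they count different things. Every DLT is a toxicity, while most toxicities are not DLTs. The stopping bullet does not say what grade, cause, period or counting unit applies.

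The lead-in sentence distinguishes non-DLT toxicity from DLT and says the former had already been seen in this cohort, so the two words cannot simply be taken as synonyms. Section 9.2 lists abdominal pain, fever, fatigue and nausea among the events expected after chemoembolization, so ordinary post-procedure events would count under a literal reading.

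The branch ends phase I and closes the route to phase II. Section 17.0 asks for conduct exactly as the approved protocol describes. A team that escalated after two non-DLT toxicities would be following one bullet and departing from the literal text of the other.

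**Working it through.** The plan states no operating characteristic for the cohort 1 rule, so there is no figure to reproduce. The check is a comparison of wording followed by a count.

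**1. What each rule in 6.6 counts**

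| Rule | Counts | Unit |
|---|---|---|
| Cohort 1, escalate | DLT | events, as worded |
| Cohort 1, stop | toxicities | not stated |
| Cohorts 2 and 3, expand | DLT | patients (1 of 3) |
| Cohorts 2 and 3, de-escalate | DLT | patients (2 of 3 to 6) |
| Cohorts 2 and 3, escalate after expansion | DLT | patients (0 or 1 of 6) |
| RP2D | first-cycle DLT | patients (at most 1 of 6) |

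The cohort 1 stopping branch is the only one of the six that does not use DLTs.

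**2. The overlap as written**

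Let d be the number of DLTs and n the number of non-DLT toxicities in cohort 1.

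- Escalate if d ≤ 1.
- Stop if d + n ≥ 2.

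Both hold when d = 0 and n ≥ 2, or when d = 1 and n ≥ 1.

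| d | n | Escalate? | Stop? |
|---|---|---|---|
| 0 | 0 or 1 | yes | no |
| 0 | 2 | yes | yes |
| 1 | 0 | yes | no |
| 1 | 1 | yes | yes |
| 2 or more | any | no | yes |

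The smallest conflicting cases are 0 + 2 and 1 + 1. No result falls outside both branches, so the fault is overlap only.

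**3. After correction**

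With the stopping bullet changed to at least two DLTs, the branches are d ≤ 1 and d ≥ 2, which are exclusive and exhaustive.

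With patient-level counting, let D be the number of the 6 patients who have a first-cycle DLT, so D runs from 0 to 6 (7 outcomes). D = 0 or 1 escalates (2 outcomes) and D = 2 to 6 stops (5 outcomes). Since 2 + 5 = 7, no outcome falls in both branches and none in neither.

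**4. Events or patients**

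The two corrections differ if one patient has two qualifying events in cycle 1 and no other patient has any. Then d = 2 (stop) but D = 1 (escalate). The rules for cohorts 2 and 3 and the RP2D rule count patients, so D is the consistent choice.

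**The case against.** The strongest reply is that context settles the meaning. The bullet sits under a heading about dose-limiting toxicities, complements the DLT branch and concludes that the MTD has been exceeded, which 6.6 determines from first-cycle DLTs. The non-DLT toxicity already observed led to a larger cohort with escalation still open, not to an automatic stop. Section 16.0 also has the Phase I disease-oriented team and the DSMC review escalation in real time. All of this stands and limits the importance of the point. It shows what was probably intended; it does not alter what the bullet says, and no other section corrects it.

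A second reply is that a broader trigger may have been intended, since the criteria arose from TACE-related toxicity and an FDA discussion whose record is not in the documents. This cannot be excluded. A broader trigger would still need a definition, and the two bullets would still overlap.

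A reader might also infer that the literal trigger makes the grade 4/5 stop redundant in cohort 1. The documents do not support that. The grade 4/5 rule runs at any time during study treatment and across cohorts. It can act on a late event in a cohort 1 patient, or on one event in cohort 1 and another in a later cohort.

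**Conclusion.** The wording is inconsistent, and the bullet should be corrected. That rests on the text of 6.6 alone and is firm. That two DLTs were meant is very probable but not proven, because intent depends partly on the FDA discussion.

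The size of the problem is a set of conflicting results, starting at 0 DLTs with two non-DLT toxicities and 1 DLT with one. A reader might want a probability that both branches are met. None is supportable: the documents give neither the number of non-DLT toxicities in cohort 1 nor rates at 200 mg after TACE. The adverse event tables in section 1.7.4 describe 600 mg in the first-in-human study of advanced solid tumors and lymphomas, not LEE011 after chemoembolization.

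Nor is this evidence of a flawed escalation design. The intended rule can be recovered from 6.6, a misreading errs toward stopping and not toward a higher dose, and the phase II sample size and power do not depend on this bullet.

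**What to change.** First, the sponsor should confirm the intended trigger against the rule discussed with the FDA. If it is DLTs, the minimal edit is to replace *At least two toxicities* with *At least two DLTs*. Preferably, reword both bullets to match the patient-level counting used elsewhere in 6.6:

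- *0-1 of 6 patients with a first-cycle DLT (Table 6.2): escalate to 400 mg.*
- *Two or more of 6 patients with a first-cycle DLT (Table 6.2): MTD exceeded; phase I stops and phase II does not open.*

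Leave severe non-DLT harm to the existing grade 4/5 stopping rule in 6.6 and 9.4, which in 6.6 already covers events related to TACE. If the sponsor finds that a broader trigger was agreed, define it by grade, attribution, window and counting unit, and limit the escalation bullet to results that do not meet it.

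If DLTs are confirmed, the cost is one or two bullets in an amendment. Design, sample size and data collection stay as they are.

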9.4 STOPPING RULES

There is no interim analysis planned.

Simmons Cancer Center Data and Safety Monitoring Board (DSMB) will oversee this study and will determine if early stoppage of the trial is needed due to unacceptable rates of drug related serious adverse events.

To assess for aggregate severe hepatobiliary toxicity and severe events that occur at any time during the study, if 2 total grade 5 or 2 grade 4 adverse events (lasting ≥ 7 days) occur while at patient is receiving study treatment and the adverse events are attributed to either being definitely, probably, or possible related to the study treatment then the study will terminate with no further patients entered.

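### In section 6.6, the third rule for cohorts 2 and 3 makes no exception for a next level that has already failed, so read literally it orders one return to 600 mg

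*Combined protocol and SAP*

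**What the plan says.** Section 6.6 sets three LEE011 levels: 200, 400 and 600 mg. Cohort 1 (200 mg) has its own rule: 6 patients, and 400 mg opens after no or one DLT. The section then states: "For Cohort 2 and 3 the following traditional 3+3 dose escalation rules will be used". Four bullets follow.

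- Bullet 1: after 1 DLT in 3, expand the same level by up to 3 patients.
- Bullet 2: after 2 DLTs in 3-6 patients, "the dose will be decreased to the previous dose level, and up to 3 additional patients will be enrolled at that dose level", to a total of 6.
- Bullet 3: when up to 3 patients have been added to a level, "if 0-1 of 6 patients has a DLT then the dose will be increased to the next dose level".
- Bullet 4: "Additional dose levels may be explored per investigator discretion to define the safety profile of the treatment".

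The RP2D is "the highest cohort level in which one or fewer subjects of 6 develops a first cycle DLT". An earlier sentence of 6.6 looks ahead to phase II: "Once the MTD is determined, patients at the MTD dose will continue with LEE011". Section 12.1 allows "3 or 6 patients in each cohort", and the Study Summary gives 9-18 patients for phase Ib. Section 16.0 has dose escalation reviewed in real time by the Phase I Disease Oriented Team (DOT) and the Data Safety Monitoring Committee (DSMC).

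**The concern.** Two different events add up to 3 patients to a level: the expansion on the way up (bullet 1) and the refill after de-escalation (bullet 2). Bullet 3 does not separate them. After an expansion, escalating on 1 DLT in 6 is ordinary 3+3 practice. After a refill, the next level up is the one that has just failed.

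At stake is avoidable exposure. Up to 3 patients, recently treated with chemoembolization, could be given a dose that has already shown two or more DLTs, and their results could not change the dose chosen for phase II.

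**Working it through.** **Inputs.** The rules and size limits are those of sections 6.6 and 12.1 and the Study Summary. The documents give no DLT rates for this combination, so every rate below is an assumption.

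**The plan's own figure.** Three levels of 3 to 6 patients give 3 × 3 = 9 to 3 × 6 = 18, which matches the stated 9-18.

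**Does bullet 3 cover the refill?** It is triggered by adding up to 3 patients, the same event that bullet 2 orders. It also names 0 of 6 as a possible result. An expansion under bullet 1 already carries one DLT, so 0 of 6 cannot follow it. Among the additions that the bullets describe, only a refill can end at 0 of 6.

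**The path, with cumulative patients.**

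1. 200 mg: 0-1/6, so 400 mg opens (6).
2. 400 mg: 0/3, so 600 mg opens (9). No bullet states this step; it comes from the 3+3 label.
3. 600 mg: two or more DLTs in the first 3 (12).
4. Bullet 2: 3 more at 400 mg, ending at 0-1/6 (15).
5. Bullet 3, literally: up to 3 more at 600 mg (18).

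**Do other limits block step 5?** Re-entry brings 600 mg to 6 patients and phase Ib to 6 + 6 + 6 = 18, so both size limits are still met. The study-wide rule in section 9.4 stops the trial "if 2 total grade 5 or 2 grade 4 adverse events" occur, with the grade 4 events lasting at least 7 days. Two grade 3 DLTs do not reach that threshold.

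**Can the extra patients matter to the RP2D?** No. With at least 2 DLTs already, 600 mg ends with at least 2 of 6, and the rule requires 1 or fewer.

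**How often does it repeat?** Once at most. After step 5, 400 mg already holds 6, so bullet 2 has no one left to add and bullet 3 cannot be triggered again.

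**Chance of reaching the state before step 5, given that 400 mg opens:**

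P = P(0/3 at 400) × P(≥2/3 at 600) × P(≤1/3 in the 400 mg refill)

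| Assumed DLT rates, 400/600 mg | Product | P |
|---|---|---|
| 5%/10% | 0.857 × 0.028 × 0.993 | 0.024 |
| 10%/15% | 0.729 × 0.061 × 0.972 | 0.043 |
| 10%/25% | 0.729 × 0.156 × 0.972 | 0.111 |
| 5%/25% | 0.857 × 0.156 × 0.993 | 0.133 |
| 10%/33% | 0.729 × 0.255 × 0.972 | 0.181 |
| 15%/50% | 0.614 × 0.500 × 0.939 | 0.288 |
| 10%/50% | 0.729 × 0.500 × 0.972 | 0.354 |

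If bullet 2 is taken to mean exactly 2 DLTs, the ends of the range become 0.857 × 0.027 × 0.993 = 0.023 and 0.729 × 0.375 × 0.972 = 0.266. If cohort 1 must also pass, the chances fall somewhat: with 10% assumed at 200 mg, the 15%/50% case goes from 0.288 to 0.255.

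**Consequence if step 5 were followed.** Expected DLTs in 3 more patients at 600 mg run from 3 × 0.10 = 0.3 to 3 × 0.50 = 1.5. The chance of at least one runs from 1 − 0.9³ = 0.271 to 1 − 0.5³ = 0.875. Weighted by the chance of reaching the state, and assuming that bullet 3 is always obeyed literally, the upper bound on extra DLTs is 0.024 × 0.3 = 0.007 (5%/10%) to 0.354 × 1.5 = 0.53 (10%/50%).

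**The case against.** The strongest reply is that this is selective literalism. The 0/3 step to 600 mg comes only from the 3+3 label, and a reader who uses that label to open the path should let it close the path too, since a conventional 3+3 does not re-enter a failed level. The RP2D sentence points the same way, as does the cohort 1 rule, under which two toxicities mean that the MTD is exceeded. Bullet 3 might also be meant only to complete bullet 1, which otherwise has no outcome rule.

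This establishes the intent, and that part stands. It does not supply the missing exception. At 0/3 the label fills a silence; at the refill it would have to override an express instruction. The reading of bullet 3 as completing bullet 1 does not account for 0 of 6. Section 17.0 requires the study to be conducted as written, so staff who rightly stopped at 400 mg would be departing from bullet 3.

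The objection to the size also stands in part. The rates are assumed, and the upper end needs a 50% DLT rate at 600 mg. Section 1.7.4 reports 600 mg as the recommended dose, below a 900 mg MTD, in the first-in-human study, although in patients with advanced solid tumors or lymphomas. Some DLTs are prolonged grade 4 events that would count toward the study-wide stop, which the calculation ignores. Section 9.4 also lets the monitoring board stop the trial for unacceptable rates of drug-related serious events.

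Four stronger readings are tempting but unsupported:

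- **An endless loop between 400 and 600 mg.** The cap of 6 at 400 mg ends it after one return.
- **A wrong phase II dose.** The RP2D rule still yields 400 mg.
- **Return after 600 mg fails in 6 patients.** Re-entry would break the limit of 6 per cohort and bring the total to 18 + 3 = 21.
- **A 2% to 35% chance that patients are re-dosed.** Those are chances of reaching the state; whether anyone is re-dosed depends on the DOT and DSMC review.

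**Conclusion.** The point holds as a minor patient-safety correction to the wording. On one path (400 mg 0/3, 600 mg failing in its first 3, 400 mg refilled to 0-1/6), bullet 3 literally orders one return to 600 mg for up to 3 patients. Neither the size limits nor, for two grade 3 DLTs, the study-wide stop prevents it. The remaining safeguard is the real-time DOT and DSMC review, which would probably work.

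The 2% to 35% range is conditional on 400 mg opening and rests wholly on assumed DLT rates of 5% to 15% at 400 mg and 10% to 50% at 600 mg. No endpoint or estimate is affected.

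**What to change.** Add to the end of bullet 3 in section 6.6: *unless that level has already had two or more DLTs, in which case the current level is the MTD/RP2D and no further patients are treated at the failed level.*

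Keep bullet 4, so that an intermediate dose below the failed level can still be explored at the investigator's discretion.

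The cost is one clause, submitted to the IRB as an amendment under section 17.3. No patients are added, and on the affected path up to 3 fewer are treated at 600 mg.
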